**Procedure for randomization (see schema on page 2):**

1. For patients making a chemotherapy treatment decision at the time of study enrollment: After study consent and the baseline assessment, the study team will then randomize the patient to either the Usual IC Arm or the Investigational IC Arm of the study using REDCap's 1:1 randomization algorithm, stratified by 1st-line or 2nd-line chemotherapy.
2. For patients NOT making a new chemotherapy treatment decision at the time of study enrollment (e.g., they are receiving ongoing treatment with first-line palliative chemotherapy), randomization will occur at the point at which the patient is faced with a new chemotherapy treatment decision (e.g., for cancer progression, or treatment-related toxicity). Research assistants will contact the treating oncologists prior to scheduled chemotherapy visits and/or restaging visits to remind them of their patient's participation on the study, and to request that the oncologist contact the research assistant in the event that a new treatment decision is being made. When the patient's oncologist confirms that the patient is faced with a new chemotherapy treatment decision, the study team will then randomize the patient to either the Usual IC Arm or the Investigational IC Arm of the study using REDCap's 1:1 randomization algorithm, stratified by 1st-line or 2nd-line chemotherapy. Patients who do not make a new treatment decision during the timeframe of this study will not be randomized, and will not complete future study assessments.

Participants will be randomized 1:1 without blinding to receive either Usual Informed Consent or Investigational Informed Consent by utilizing a randomization algorithm managed by REDCap. This will be stratified according to whether the patient is 1st line palliative chemotherapy or 2nd line palliative chemotherapy.

The name and telephone number of the research study person who will be responsible for registration and randomization is: [name], [[name]\\[contact]](mailto:[contact]), [contact].

When registering subjects, the study team will ask for the following information (see Appendix B):

- Name, telephone number, and email address of research assistant enrolling the participant
- Date subject signed informed consent

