### **Participating sites should follow their own institutional practices for usual informed consent.**

Patients randomized to Interventional IC Arm will be given regimen specific written and video Informed Consent tools developed by the study team. The treating oncologist will identify which chemotherapy regimen(s) are being considered, in order to select the appropriate informed consent (IC) tool(s) to give the patient. The patient may be given more than one IC tool if relevant; for example: if they are deciding between FOLFOX and FOLFIRI, they could be given both IC tools. Patients randomized to the intervention arm may receive the intervention in addition to OR in place of the

**Title:** Improving Informed Consent for Palliative Chemotherapy: RCT of Usual IC versus Investigational IC

**Overall PI:** [name], Dana-Farber Cancer Institute

**Dana-Farber protocol version no./date:** v17 / August 30, 2017

standard institutionally approved chemotherapy information sheets (both are acceptable); this is at the discretion of the treating site or the treating physician. Patients randomized to the Interventional IC Arm will undergo informed consent for chemotherapy. This will include receipt of the investigational IC tool for chemotherapy in addition to OR in place of the standard institutionally approved chemotherapy teaching sheet.

At the beginning of the study period, the video and booklet informed consent tools will be shared with medical oncologists and nurse practitioners at a GI oncology staff meeting. The purpose of this orientation is to help facilitate any subsequent conversations about the study informed consent (IC) tools that might occur between providers and patients randomized to the intervention.

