*Hypothesis:* Patients randomized to the intervention will be more likely to discuss their end-of-life care preferences with their healthcare proxy, and with their oncologist as compared to patients randomized to the usual IC process.

We will adhere to standard reporting principles delineated by the CONSORT statement for conduct and reporting of randomized trials. Primary reports will reflect the as randomized, "intention to treat" principle, however, we will also describe results according to actual exposure to the study interventions (based on patients' self-report of whether they reviewed the standard-of-care, or investigational chemotherapy informed consent materials). Fisher's exact test will test the difference between the study arms in the first primary outcome (the proportion of patients at follow-up assessment who fail to understand that chemotherapy is "not at all likely" to cure their cancer, as assessed by an item from CANCORS). We will also test the influence of the intervention on secondary outcomes (e.g. understanding of the goal of palliative chemotherapy, chemotherapy risks, decisional conflict,

**Title:** Improving Informed Consent for Palliative Chemotherapy: RCT of Usual IC versus Investigational IC

**Overall PI:** [name], Dana-Farber Cancer Institute

**Dana-Farber protocol version no./date:** v17 / August 30, 2017

achievement of preferred role in decision-making, satisfaction with chemotherapy IC process, prognostic understanding, advance care planning, discussion of end-of-life care preferences, satisfaction with MD communication, satisfaction with informed consent (IC) documents, decisional regret, emotional distress) using Fisher's exact or chi-square tests for dichotomous outcomes, and t-tests or Wilcoxon tests for linear outcomes. For missing data for primary or secondary outcomes, we will employ multiple imputation under a missing at random assumption.

Subset analyses will explore the effect of the intervention on 1) patients making a decision about 1st line treatment, 2) patients making a decision about 2nd line treatment, 3) patients with colorectal cancer, and 4) patients with pancreatic cancer.

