Because the effects of our intervention may be moderated by patient characteristics (e.g. age, race/ethnicity, health literacy and numeracy, communication preferences, decisional control preferences), we plan to conduct exploratory analyses investigating whether these factors moderate the effect of the intervention on outcomes including 1) accurate understanding of chemotherapy benefits, 2) satisfaction with communication and the IC tools, 3) decisional involvement, or 4) emotional distress. For example: we hypothesize that the IC tool may lead to decreased distress among patients who prefer a detail-oriented prognostic communication style, whereas it may lead to increased distress among patients who prefer a vague and support-focused prognostic communication style. We would also hypothesize that the effects of

**Title:** Improving Informed Consent for Palliative Chemotherapy: RCT of Usual IC versus Investigational IC

**Overall PI:** [name], Dana-Farber Cancer Institute

**Dana-Farber protocol version no./date:** v17 / August 30, 2017

the intervention may be greater among patients with higher health literacy scores. We will test these hypotheses using multivariable logistic or linear regression analyses (depending upon the dependent variable), including interaction terms for collinear factors, and controlling for potential confounding factors (e.g. age, race/ethnicity, marital status).

**Power:** In the CANCORS study, 80% of mCRC patients on 1st line chemotherapy thought that chemotherapy could potentially cure their disease (median of 4 months post-diagnosis). Based on previous series and projections about our patient mix, we anticipate that 60% of patients will have inaccurate expectations about the benefits of chemotherapy. If the intervention strategy is able to better align expectations with likely outcomes by one third (33%) we will deem the intervention as having major impact. If this benchmark 33% reduction is not achieved but the intervention exposed subjects nonetheless have expectations that are more accurate, we will view the intervention as beneficial but lacking major impact. Assuming a baseline 60% rate of inaccurate expectations about the benefits of chemotherapy, with a total of 194 patients, we will have 80% power to detect a 33% decrease (20% absolute decrease) in inaccurate expectations among patients exposed to the intervention with a one-sided type I error of 2.5%.

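### The primary Fisher's exact test uses no strata, not even the line of therapy used to randomize; this costs precision but causes no bias

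*Combined protocol and SAP*

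**What the plan says.** The randomization procedure in section 4.0, repeated in section 5.5, assigns patients "using REDCap's 1:1 randomization algorithm, stratified by" first- or second-line chemotherapy. No other factor is named.

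Section 3.0 admits metastatic colorectal, locally advanced pancreatic and metastatic pancreatic cancer.

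Section 5.3 lets the comparator vary: "Participating sites should follow their own institutional practices for usual informed consent". In the intervention arm the tools may supplement or replace the standard information sheets, and "this is at the discretion of the treating site or the treating physician".

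Section 6.0 states that "Fisher's exact test will test the difference between the study arms in the first primary outcome". It names no stratum or covariate for that test. Subsets by line and by cancer type are exploratory, and covariates enter only the exploratory moderator models. No analysis by site, or adjusted for site, is planned.

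**The concern.** Line, cancer type and site are all known before randomization, and the protocol gives reason to think the last two could predict the primary answer. The 60% control rate in section 6.0 rests partly on projections about patient mix, against 80% for colorectal patients in the cited survey. Section 1.2 reports 81% v 69% inaccurate belief in two cancer types. Those are colorectal and lung, so they show only that the rate can differ by cancer type. Site determines what usual consent consists of.

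A test that ignores such groups leaves their between-group variation in the error term. Leaving out a factor used to stratify the randomization also discards information the design has already collected. The endpoint is one dichotomized item in an unblinded trial, so any adjustment chosen after an imbalance is seen would be open to challenge. What is at stake is power and the credibility of any later adjustment. The validity of the randomized comparison is not in question.

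**Working it through.** **Inputs from section 6.0.** "Assuming a baseline 60% rate of inaccurate expectations about the benefits of chemotherapy"; a 20-point absolute reduction, so 60% v 40%; 80% power; "with a total of 194 patients" (97 per arm); and a test "with a one-sided type I error of 2.5"%. The sidedness of Fisher's test is not stated separately, so I take it as one-sided at 2.5%, to match.

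**1. The plan's own figure.** With pooled variance and no continuity correction, n per arm = [1.96·√(2·0.5·0.5) + 0.8416·√(0.6·0.4 + 0.4·0.6)]² / 0.2² = (1.386 + 0.583)² / 0.04 = 96.9. This rounds up to 97 per arm, 194 in total, with power 80.0%. The stated size reproduces.

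**2. Power of the test actually planned.** Summing exact binomial probabilities over all tables that Fisher's test rejects at 0.025 gives 76.4% at 97 per arm. The shortfall is 80.0 − 76.4 = 3.6 points, all from the conservatism of the exact test.

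**3. Does ignoring the groups distort the test?** In a simulation with a factor in 40% of patients and an outcome gap of 20 or 30 points (both assumed), with that factor left unstratified, Fisher's one-sided type I error is about 1.7%. It is not inflated.

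**4. How far can chance imbalance move the result?** With equal arms at 194, the between-arm difference in a factor's share is hypergeometric. The shares below are assumed.

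| Share of patients with the factor | SD of difference (points) | Chance of 10 points or more |
|---|---|---|
| 50% | 7.2 | 15% |
| 30% | 6.6 | 16% |
| 20% | 5.8 | 7% |
| 10% | 4.3 | 1% |

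Shift in the arm difference = imbalance × outcome gap. At a 20-point gap, a 10-point imbalance shifts it by 0.10 × 20 = 2 points. A 12:8 split of 20 patients gives (4/97) × 20 = 0.8 points, and a 30:20 split of 50 gives (10/97) × 20 = 2.1 points. The target effect is 20 points.

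**5. What comparing within groups gains.** For two equal groups averaging 60%, variance ratio = mean of p(1 − p) within groups / 0.24:
- 50% v 70%: (0.25 + 0.21)/2 = 0.230, ratio 0.958, a 4.2% cut.
- 45% v 75%: (0.2475 + 0.1875)/2 = 0.2175, ratio 0.906, a 9.4% cut.
- 40% v 80%: (0.24 + 0.16)/2 = 0.200, ratio 0.833, a 16.7% cut.

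**6. Power of the stratified test.** The Mantel-Haenszel statistic is z = Σ(x₀ₖ − n₀ₖmₖ/Tₖ) / √Σ[n₀ₖn₁ₖmₖ(Tₖ − mₖ)/(Tₖ²(Tₖ − 1))]. In stratum k, x₀ₖ is the number of inaccurate control answers, n₀ₖ and n₁ₖ are the arm sizes, mₖ is all inaccurate answers and Tₖ is all patients. Reject if z ≥ 1.96. The simulation uses 97 per arm and eight strata (line × cancer type × site group), with assumed shares and gaps.

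| Outcome gap between groups | Fisher, unstratified | Mantel-Haenszel |
|---|---|---|
| none | about 76% | about 78% |
| 20-30 points | about 76% | about 80-83% |

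The Mantel-Haenszel one-sided type I error is near 2.5%.

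**7. The alternative of changing the allocation.** Stratifying the randomization by the 40% factor in step 3 while keeping Fisher's test gains about 0.5 to 1.5 points of power at gaps of 20-30 points.

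**The case against.** The strongest reply is that chance imbalance is ordinary sampling error, already covered by the p-value, and that an unadjusted test in a randomized trial is valid. That stands in full: steps 3 and 4 show no inflation and shifts of about 1-2 points.

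A second reply is that much of the gain comes from leaving Fisher's test rather than from stratifying. This is also fair. Against the uncorrected pooled test at 80.0%, eight uninformative strata cost about 2 points (78% v 80%), and informative ones gain 0 to 3 (80-83% v 80%). Against the test the plan names, the gain is about 2 to 7 points.

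Third, enrolment may reach 244 patients (section 5.1), and if all 244 were analysed Fisher's power would be about 85%. But section 4.0 says some enrolled patients will never be randomized, and the plan's power statement is for 194.

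A reader might also infer three stronger things that the documents do not support:
- *The cancer-type subsets are compromised.* Cancer type is constant within each subset, so it cannot confound the comparison there. Each subset remains randomized, and even a 60:40 split keeps 4 × 0.6 × 0.4 = 96% of the efficiency. The subsets are also only exploratory.
- *Stratifying by site would control whether the tools add to or replace the standard sheets.* That choice may be the physician's as well as the site's, and it arises only in the intervention arm. Balance by site would not remove it.
- *Site-specific usual consent is itself a flaw.* A local usual-care comparator is a legitimate pragmatic choice, and section 6.0 already plans results by self-reported exposure.

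**Conclusion.** The point holds as a modest, inexpensive gain in precision. The primary test discards the randomization stratum and two other factors known at entry. At 194 patients its power is about 76%. A stratified Mantel-Haenszel test would have about 78% if the factors prove uninformative and about 80-83% if outcome rates differ by 20-30 points between groups, with type I error near 2.5%.

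The 76% rests only on the plan's own inputs and a one-sided 2.5% test. The stratified figures rest on assumed gaps and shares, because the documents give no number of sites, no site or cancer-type shares and no outcome rate for pancreatic cancer. Nothing here supports a finding of bias or of an inflated false-positive rate.

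**What to change.** In section 6.0, define the primary comparison as a one-sided 2.5% Mantel-Haenszel test, with the Mantel-Haenszel risk difference and confidence interval, stratified by line of therapy and cancer type. Add Dana-Farber v other sites if numbers allow, under a rule fixed before outcomes are compared by arm. Keep the unadjusted Fisher's exact test as a sensitivity analysis.

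Leave the REDCap allocation table unchanged. The protocol is at v17, and section 5.5 describes participants already raising issues in the surveys, so the trial appears to be under way. A new table would mix allocation schemes for a gain of only 0.5 to 1.5 points.

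The cost is a short text change, with no extra patients, visits or data. The downside is up to 2 × 2 × 2 = 8 strata, some sparse. Mantel-Haenszel methods tolerate this, although a stratum with patients in only one arm contributes nothing. Using line and cancer type alone (four strata) limits that loss.

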- Subject and caregiver's phone numbers, emails, and postal mail addresses (reason for collecting these: so central research assistant at Dana-Farber can administer follow-up assessments)
- Subject and caregiver's ranks of preference regarding contact method
- Subject and caregiver's genders
- Subject and caregiver's initials
- Subject and caregiver's ages
- Subject ID number
- Primary oncologist
- Confirmation of eligibility
- Stratification or classification factors (1st versus 2nd line palliative chemotherapy)

**Procedure for assessment contact and reminders:** It is acceptable to administer each assessment aloud (via phone or in-person), via email (REDCap weblink), via iPad (REDCap), or via hard copy (in-person or postal mail). The baseline assessment will be administered immediately after the participant signs informed consent; the baseline caregiver assessment will be administered immediately after the caregiver receives the

**Title:** Improving Informed Consent for Palliative Chemotherapy: RCT of Usual IC versus Investigational IC

**Overall PI:** [name], Dana-Farber Cancer Institute

**Dana-Farber protocol version no./date:** v17 / August 30, 2017

study letter and agrees to participate. In rare cases when immediate administration is not possible, the central study research assistant at Dana-Farber will follow-up with the participant up to 3 times post-informed consent. One follow-up is defined as: an in-person approach OR a phone call with an accompanying email. If the participant is non- responsive after 3 attempts, then the study research assistant will mark the baseline assessment as missing and will not contact the participant about the baseline assessment again.

The post-decision assessment will be administered by the central study research assistant at Dana-Farber at any point between the day the participant starts chemotherapy and 4-weeks post-chemo start. During this 4 week period, the study research assistant will follow-up with the participant up to 3 times. One follow-up is defined as: an in-person approach OR a phone call with an accompanying email. If the participant is non- responsive after 3 attempts, then the study research assistant will mark the post-decision assessment as missing and will not contact the participant about the post-decision assessment again.

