The follow-up assessment will be administered by the central study research assistant at Dana-Farber at any point between 2 months post-chemo start and 3 months post-chemo start. During this 1 month period, the study research assistant will follow-up with the participant and caregiver up to 3 times each. One follow-up is defined as: an in-person approach OR a phone call with an accompanying email. If the participant is non- responsive after 3 attempts, then the study research assistant will mark the follow-up assessment as missing and will not contact the participant about the follow-up assessment again.

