### 5.2 Selection of Instruments

Questionnaire-based instruments will be administered 1) in person by a trained research assistant at the time of a routinely scheduled visit, 2) by e-survey, 3) by phone, , or 4) by postal mail. Mode of collection will be recorded. REDCap (Research Electronic Data Capture) will be used to collect and store all participant information and survey answers. REDCap is a secure, web-based, HIPAA-compliant application hosted by the Partners HealthCare Research Computing, Enterprise Research Infrastructure & iServices (ERIS) group, designed to support data capture for research studies, providing: 1) an intuitive interface for validated data entry; 2) audit trails for tracking data manipulation and export procedures; 3) automated export procedures for seamless data downloads to common statistical packages; and 4) procedures for importing data from external sources.

Regardless of whether a participant is randomized to receive Usual IC materials or the Interventional IC materials, each participant will be asked complete three assessments:

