### **Instrument 2: Post-Decision Assessment (See Appendix E and Appendix F)**

Within 0-4 weeks of the participant's treatment decision, the participant will be asked to complete a post-decision survey assessing core understanding required for informed consent (IC) (risks, benefits, alternatives), understanding of illness (diagnosis, curability), decisional conflict, satisfaction with the IC materials, satisfaction with communication, and anxiety. The post-decision assessment takes approximately 20 minutes to complete.

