### **Instrument 3: Follow-up Assessment (See Appendix G and Appendix I)**

Within 2-3 months of the participant's treatment decision, the participant will be asked to complete a follow-up survey assessing changes in treatment and illness understanding, decisional regret, communication satisfaction, care satisfaction & anxiety. The post-decision assessment takes approximately 20 minutes to complete.

**NOTE:** Participants will be asked questions about prognosis regardless of whether or not they skip the life expectancy sections in the booklet and video.

Immediately following completion of the follow up assessment: Using methods similar to those described by White et al, the interviewer will show each participant his/her responses to the 2 questions about prognosis\*\*. Next, the interviewer will read the following standardized prompt: "Please take a moment to look at your responses. I notice that your answers to these two questions are [different/the same]. Can you tell me a little bit about this?"

The research assistant will then ask permission to audio-record the patient's answers. If the participant is willing to answer the question but declines audio-recording, notes will be taken during and after the interview. The RA will use standard cognitive interviewing techniques, such as reflexive listening, "think alouds" and standard probes ("can you tell me what you mean by that?") as necessary.

*\*\*Copy-pasted for reference - these are the 2 questions about prognosis:*

*Q: Based on what you have learned or been told, what is your understanding about how long the typical person with your type of cancer can expect to live?*

*A: 1, More than 10 years | 2, More than 5, but less than 10 years | 3, More than 3, but less than 5 years | 4, More than 2, but less than 3 years | 5, More than 1, but less than 2 years | 6, Less than 1 year*

*Q: Every person is different and every situation is unique. If you had to make a guess - based on what you have learned about your cancer, your cancer treatment, and what you know about yourself - how long do you think that you have to live?*

*A: 1, More than 10 years | 2, More than 5, but less than 10 years | 3, More than 3, but less than 5 years | 4, More than 2, but less than 3 years | 5, More than 1, but less than 2 years | 6, Less than 1 year*

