**Medical Record Abstraction (see Appendix K):** Research assistants will perform medical record abstraction. These medical record abstractions will be designed to assess relevant information about their clinical condition (e.g. stage at diagnosis, date of recurrence, performance status, comorbid conditions), treatment decision, and treatment experience. Information will be entered into a study specific structured medical record abstraction tool (Appendix K). See below for specific information

**Title:** Improving Informed Consent for Palliative Chemotherapy: RCT of Usual IC versus Investigational IC

**Overall PI:** [name], Dana-Farber Cancer Institute

**Dana-Farber protocol version no./date:** v17 / August 30, 2017

to be abstracted:

- date of diagnosis; stage at diagnosis; prior adjuvant or palliative chemotherapy; date of metastatic recurrence (if relevant); comorbid medical conditions; performance status; treatment decision made (e.g., what chemotherapy regimen, clinical trial, no chemotherapy); changes in treatment (e.g. dose reductions, change in chemotherapy); results of restaging scans (disease progression, stable disease, or response); changes in treatment; medical record documentation of advance care planning; and vital status at study completion.

**NOTE:** Each site has the option to conduct the medical record review for their site's participants using the unique study ID # and enter the information into REDCap using the participants' unique study ID #. Medical records from participating sites will not be released to Dana-Farber unless the participant signs the medical record release form (Appendix X).

In some cases, a participant will consent to participate in this study and begin this study while at a participating site, but then continue/transfer care at a non-participating site. In these instances, the participant will be asked to sign an optional, voluntary Global Medical Record Release Form (see Appendix X) so that the central research assistant at Dana-Farber can access the participant's medical records in order to complete the study Medical Record Abstraction (Appendix K).

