In cases in which the study research assistant gives the participant the investigational IC booklet and video, research assistants will make it clear that their sole purpose is to orient the patient to the booklet/video and answer questions regarding how to access the video website and/or use the study iPad to watch the video. If the participant asks the study research assistant any question

**Title:** Improving Informed Consent for Palliative Chemotherapy: RCT of Usual IC versus Investigational IC

**Overall PI:** [name], Dana-Farber Cancer Institute

**Dana-Farber protocol version no./date:** v17 / August 30, 2017

about information presented in the investigational IC tools, the research assistant will refer the patient back to their primary oncologist, nurse practitioner, or infusion nurse.

6. **ADMINISTER POST-DECISION ASSESSMENT** within 0-4 weeks by the central research assistant at Dana-Farber after the day on which the participant made their treatment decision and initiated their new chemotherapy treatment. Questionnaire- based instruments will be administered 1) in person by a trained research assistant at the time of a routinely scheduled visit, 2) by e-survey, 3) by phone, 4) or by postal mail. Mode of collection will be recorded. The post-decision assessment takes approximately 20 minutes to complete.
7. **ADMINISTER FOLLOW-UP ASSESSMENT** within 2-3 months by the central research assistant at Dana-Farber after the day on which the participant made their treatment decision and initiated their new chemotherapy regimen. Questionnaire- based instruments will be administered to the participant and his/her caregiver 1) in person by a trained research assistant at the time of a routinely scheduled visit, 2) by e-survey, 3) by phone, 4) or by postal mail. Mode of collection will be recorded. The follow-up assessment takes approximately 20 minutes to complete.

**PATIENT:** Immediately following completion of the follow up assessment: Using methods similar to those described by White et al, the interviewer will show each participant his/her responses to the 2 questions about prognosis\*\*. Next, the interviewer will read the following standardized prompt: “Please take a moment to look at your responses. I notice that your answers to these two questions are [different/the same]. Can you tell me a little bit about this?”

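### Sections 4.0 and 5.5 open the outcome surveys only once chemotherapy starts, while 5.2 times them from the decision, so randomized patients who choose no chemotherapy may have no observed primary outcome

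*Combined protocol and SAP*

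**What the plan says.** Three sections time the same two patient surveys.

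- **Section 4.0, Procedure for assessment contact and reminders.** The post-decision survey is given "at any point between the day the participant starts chemotherapy and 4-weeks post-chemo start". The follow-up survey is given "at any point between 2 months post-chemo start and 3 months post-chemo start", and contact attempts in that month cover the caregiver as well.
- **Section 5.5, steps 6 and 7.** The same lengths of window (0-4 weeks, 2-3 months) are counted from a joint event. For the follow-up survey this is "after the day on which the participant made their treatment decision and initiated their new chemotherapy regimen".
- **Section 5.2, Selection of Instruments.** Whatever the arm, "each participant will be asked complete three assessments". The post-decision survey falls "Within 0-4 weeks of the participant's treatment decision" and the follow-up survey "Within 2-3 months of the participant's treatment decision". The caregiver follow-up has the same decision-based window.

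Section 5.4 fixes the follow-up assessment as the time point for the primary outcome. Section 6.0 promises an as-randomized primary report, with multiple imputation under missing at random for missing outcomes.

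The chart abstraction described in 5.2 lists the possible treatment decisions as "what chemotherapy regimen, clinical trial, no chemotherapy", and 5.7 repeats this. The only group said to skip later surveys is in 4.0: patients who make no new treatment decision during the study, who "will not be randomized, and will not complete future study assessments".

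**The concern.** Patients are randomized while they are still deciding about treatment (3.0, 4.0). The tools are normally handed over before the decision is made (5.3, 5.5), and they name palliative or supportive care among the alternatives (5.3). Whether a patient starts chemotherapy is therefore settled after randomization, and the intervention could affect it.

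If staff follow the contact rule in 4.0, a patient who never starts has no date from which either window can open. Both the follow-up answer and the post-decision answer to the same item would be absent. Whether the primary outcome is collected would then depend on a choice made after randomization.

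The belief being measured may also bear on that choice. Section 1.2 argues that over-optimistic expectations promote the use of late-line chemotherapy. That statement concerns late-line treatment and this trial covers first and second line, but it makes missing at random an assumption to defend for this group. Any imputation model would have to learn how follow-up answers relate to other variables from patients who started.

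**Working it through.** **Step 1. Set the anchors side by side for a randomized patient who chooses no chemotherapy.**

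| Section | Start of the clock | Does a window open? |
|---|---|---|
| 4.0 | chemotherapy start | no |
| 5.5, steps 6 and 7 | decision made and chemotherapy initiated | no, the second condition is never met |
| 5.2 | treatment decision | yes |

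For a patient who decides and starts within days, all three give nearly the same dates. The conflict matters for non-starters and, to a lesser degree, for delayed starters.

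**Step 2. Check that the case is foreseen and not excluded.** No chemotherapy is a recorded decision (5.2, 5.7). The skip rule in 4.0 covers only patients who are never randomized. The available text gives no window for a randomized non-starter under 4.0 or 5.5, and does not say which section governs.

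**Step 3. Reproduce the planned sample size, to get the arm size.** Inputs from 6.0: 60% inaccurate under usual consent, a 20-point absolute decrease (to 40%), one-sided 2.5%, 80% power. With the pooled normal approximation:

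n per arm = [1.960 × √(2 × 0.5 × 0.5) + 0.842 × √(0.6 × 0.4 + 0.4 × 0.6)]² / 0.20² = (1.386 + 0.583)² / 0.04 = 96.9

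This rounds to 97 per arm, or 194 in total, as stated. The figure is not in dispute. It supplies the denominator below.

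**Step 4. Bound the effect without assuming what decliners believe.** If k of n randomized patients in an arm have no observed answer, the number inaccurate among them lies between 0 and k. The arm's as-randomized rate is therefore undetermined by k/n, and the difference between arms by the sum of the two ranges.

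- One decliner: 1/97 = 1.03 points. If all 244 patients in 5.1 were randomized (122 per arm), 1/122 = 0.82 points.
- The numbers of decliners below are assumptions, since the documents give none:

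| Decliners in each arm | Difference undetermined by, 97 per arm | 122 per arm |
|---|---|---|
| 1 | 2/97 = 2.1 points | 2/122 = 1.6 points |
| 2 | 4/97 = 4.1 points | 4/122 = 3.3 points |
| 5 | 10/97 = 10.3 points | 10/122 = 8.2 points |

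**Step 5. Check whether a direction can be given.** If p is the true rate over all randomized patients, d the share declining and q the share of decliners who are inaccurate, the rate among starters is (p − d × q)/(1 − d). Take p = 0.60 and 0.40, with assumed decline of 3% (usual) and 10% (intervention):

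- all decliners accurate (q = 0): 0.60/0.97 − 0.40/0.90 = 61.9% − 44.4% = 17.4 points;
- all decliners inaccurate (q = 1): 0.57/0.97 − 0.30/0.90 = 58.8% − 33.3% = 25.4 points.

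The true difference is 20 points in both cases. The error can go either way, so no direction can be stated.

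**The case against.** The strongest reply is that 5.2 already answers the question: it surveys everyone and counts from the decision, which a decliner does have. On that reading 4.0 and 5.5 are contact logistics written for the usual patient, who decides and then starts. The schema, the survey forms, the site checklist and the phone script (Appendices E to J, A and M) were not in the text available and may contain a rule for non-starters. Eligibility also requires that the oncologist recommended considering a study regimen, so decliners may be rare.

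Much of this stands. It shows the likely intent, and it is why the consequence is stated only for the case that 4.0 or 5.5 is followed. It does not remove the conflict: 4.0 is the section that tells staff when to contact patients, and its rule differs from 5.2.

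Three stronger readings are tempting and not supported.

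- A reader might infer that decliners drop out of the primary analysis. They would not, because 6.0 would impute them. What they would lack is an observed outcome.
- A reader might infer that nothing usable is known about them. Section 5.4 says the primary item is also asked at baseline, and the imputation model in 6.0 is not specified, so baseline variables could enter it. They would inform the imputation, but the link to the follow-up answer would still be estimated in starters.
- A reader might infer a definite bias or loss of power. Any such figure needs a decline rate and the beliefs of decliners, and the documents give neither.

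**Conclusion.** The point holds in conditional form and should be fixed. The sections disagree on when the outcome surveys are due. Under 4.0 or 5.5, a randomized patient who starts no chemotherapy has no observed primary outcome, for a reason that arises after randomization and that the intervention could influence. The planned imputation would then rest on an assumption that is open to doubt for this group, although the answer could simply be collected.

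The only figure that needs no assumption about beliefs is the bound of about 1 point in an arm's rate per decliner, taking 97 per arm from 6.0. Whether the total is trivial or material against the 20-point target depends on a decline rate that is not given. The conclusion also assumes that no unseen appendix or schema already sets a window for non-starters.

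**What to change.** - Reconcile 4.0 and 5.5 with 5.2 so that every randomized patient has a window for both surveys. Keep the 0-4 week and 2-3 month lengths. Count from the treatment-decision date, or from the randomization date if no decision date is recorded, at least for patients who do not start chemotherapy.
- State that randomized non-starters complete both surveys, including the primary item, and that their caregivers complete the caregiver follow-up on the same basis.
- Mark the regimen-specific risk items and the active-treatment communication items (both in 5.4) not applicable for non-starters.
- Report by arm the number who did not start chemotherapy and the number without an observed primary outcome.

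The cost is one clarifying amendment, not-applicable rules for two sets of items, and a few extra surveys by the central research assistant. If all patients are re-anchored to the decision date, those with a delayed start are surveyed slightly earlier relative to treatment. Limiting the new anchor to non-starters avoids that.
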